8 SAFETY AND TOLERABILITY

All safety analyses will be conducted in the Safety population. Safety parameters include adverse events (AEs), vital signs, and clinical laboratory parameters.

8.1 Adverse Events

Verbatim descriptions of AEs will be coded using Version 17.1 or higher of MedDRA. Summary tables will be provided for all treatment-emergent adverse events (TEAEs), but all AEs will be provided in a listing. A treatment-emergent AE is defined as any AE that newly appeared, increased in frequency, or worsened in severity on or after the initiation of active test article. An AE is considered treatment emergent if the AE start date and time is on or after the start date and time of the first dose of active test article. If time of the AE is missing and it occurred on the same date as the first dose of active test article, the AE will be defined as treatment emergent. If the start date of the AE is partial or missing and it cannot be determined if the AE occurred prior to or after the first dose of test article, the AE should be defined as treatment emergent.

An overall summary of AEs will include the number of subjects who experienced at least one AE of the following categories: any AE, any TEAE, any drug-related TEAE, any severe TEAE, any serious TEAE, any drug-related SAE, any serious TEAE leading to death, any TEAE leading to premature discontinuation of test article, any TEAE leading to premature discontinuation from the study, any TEAE leading to dose interruption of test article, and any serious TEAE leading to premature discontinuation of test article.

The number and percentage of subjects reporting a TEAE will be tabulated by system organ class and preferred term; by system organ class, preferred term, and severity (mild, moderate, and severe); and by system organ class, preferred term, and relationship (unrelated or related to test article). The incidence of TEAEs will be summarized by preferred term, sorted by decreasing frequency, for all TEAEs, related TEAEs, serious TEAEs, and TEAEs leading to study drug discontinuation. The incidence of serious TEAEs, TEAEs leading to premature discontinuation of test article, and TEAEs leading to a dose interruption of test article will be summarized by system organ class and preferred term. For all analyses of TEAEs, if the same AE (based on preferred term) is reported for the same subject more than once, the AE is counted only once for that preferred term and at the highest severity and strongest relationship to test article.

In addition, all AEs (including non-TEAEs), serious TEAEs, TEAEs leading to discontinuation of test article, and TEAEs leading to dose interruption of test article will be provided in listings by subject, verbatim term, MedDRA system organ class and preferred term, start and end date, seriousness flag, severity, relationship to test article, relationship to study protocol, action taken with test article, non-test article action taken and outcome.

8.2 Vital Signs

Vital signs include blood pressure (BP), heart rate, pulse oximetry, RR, and body temperature.

Descriptive statistics of the change from baseline to each post-baseline time point and the highest and lowest post-baseline value will also be provided. Baseline is defined as the value closest to but prior to the initiation of test article administration.

Post-baseline vital signs will be defined as clinically notable (CN) if they meet the criterion value or both the criterion value and the change from baseline criterion listed in Appendix 4. The incidence of CN vital signs will be summarized by time point and will be listed and flagged in by-subject listings. The overall post-baseline incidence of CN values for each vital sign parameter, which includes values from unscheduled post-baseline visits, will also be summarized. A listing will also be provided of subjects with a CN vital sign and will list all values for a vital sign noted as CN.

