6.2 Inclusion and Exclusion Criteria

Each subject must meet all of the following criteria to be enrolled in this study:

Main Criteria for Inclusion:

- 1. Written and signed informed consent must be obtained before any protocol specific assessment is performed.
- 2. Male or female, age 18 years or older.
- 3. Has at least 3 of the following symptoms:
 - Cough
 - Production of purulent sputum
 - Dyspnea (shortness of breath)
 - Pleuritic chest pain
- 4. Has at least TWO of the following abnormal vital signs:
 - Fever or hypothermia documented by the investigator (temperature > 38.0°C [100.4°F] or < 36.0°C [95.5°F])
 - Hypotension with systolic blood pressure (SBP) < 90 mm Hg
 - Heart rate > 90 beats per minute (bpm)
 - Respiratory rate (RR) > 20 breaths/minute
- 5. Has at least 1 clinical sign or laboratory finding associated with CABP:
 - Hypoxemia (partial pressure of arterial oxygen [PaO₂] < 60 mm Hg by arterial blood gas [ABG] or oxygen saturation < 90% by pulse oximetry)
 - Physical examination findings of pulmonary consolidation (eg, dullness on percussion, bronchial breath sounds, or egophony)
 - An elevated total white blood cell (WBC) count (> 12,000 cells/mm³) or leucopenia (WBC < 4,000 cells/mm³) or elevated immature neutrophils (> 15% band forms), see % bands calculation in Appendix 2 (regardless of total peripheral WBC count)
- 6. Has disease categorized as being PORT Risk Class II or III at Screening where initiation of antibiotics with oral therapy is appropriate in the opinion of the investigator, whether inpatient or outpatient setting (see PORT Risk Class calculation in Appendix 4).

- 7. Radiographically-confirmed pneumonia, ie, new or progressive pulmonary infiltrate(s) on chest X-ray (CXR) or chest computed tomography (CT) scan consistent with acute bacterial pneumonia within 48 hours prior to the first dose of test article.
- 8. Ability to swallow up to 3 tablets in succession.
- 9. Females must have a negative urine pregnancy test at Screening and agree to comply with using an acceptable method of birth control as per your local requirements (eg, abstinence, oral contraceptive, intrauterine device [IUD], barrier contraception [condom], tubal ligation, hysterectomy, bilateral oophorectomy, postmenopausal, or vasectomized partner) from Screening through PTE. Males must agree to use an acceptable method of birth control with female partner(s) and must not donate sperm from Screening through PTE.

Main Criteria for Exclusion:

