10.4 Clinically Notable Values

- Clinically notable laboratory parameters, meeting predefined criteria as values with 2 grade increases will be listed
- Clinically notable vital signs, meeting predefined criteria as specified in Appendix 4 by time point measured

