Appendix 4 Criteria for Clinically Notable Vital Signs

Vital Sign Parameter	Flag	Criterion Value	Change from Baseline
Systolic Blood Pressure (mmHg)	High (CH)	≥ 180	Increase of $\geq 20 \text{ mmHg}$
	Low (CL)	≤ 90	Decrease of $\geq 20 \text{ mmHg}$
Diastolic Blood Pressure (mmHg)	High (CH)	≥ 105	Increase of $\geq 15 \text{ mmHg}$
	Low (CL)	≤ 50	Decrease of $\geq 15 \text{ mmHg}$
Heart Rate (bpm)	High (CH)	≥ 120	Increase of ≥ 15 bpm
	Low (CL)	≤ 50	Decrease of ≥ 15 bpm

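### The clinically notable vital-sign rule in SAP 8.2 reduces to the criterion value alone, so the Appendix 4 change-from-baseline column never acts

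*SAP*

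**What the plan says.** Protocol 12.6.1 leaves the criteria for clinically notable vital signs to the SAP. SAP 8.2 applies the flag to post-baseline values, "if they meet the criterion value or both the criterion value and the change from baseline criterion listed in Appendix 4". For this purpose, "Baseline is defined as the value closest to but prior to the initiation of test article administration".

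Appendix 4 of the SAP covers three parameters, each with a high and a low row, and every row has both a criterion value and a change criterion:

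| Parameter | High: value, change | Low: value, change |
|---|---|---|
| SBP (mmHg) | ≥ 180, rise ≥ 20 | ≤ 90, fall ≥ 20 |
| DBP (mmHg) | ≥ 105, rise ≥ 15 | ≤ 50, fall ≥ 15 |
| Heart rate (bpm) | ≥ 120, "Increase of ≥ 15 bpm" | ≤ 50, "Decrease of ≥ 15 bpm" |

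SAP 10.4 returns to the subject only by reference: "Clinically notable vital signs, meeting predefined criteria as specified in Appendix 4 by time point measured". It does not say how the two columns combine.

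The CN flag feeds an incidence summary by time point, an overall post-baseline incidence that includes unscheduled visits, and a listing of subjects with a CN value.

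**The concern.** A table that gives a change threshold in every row implies that the change is meant to matter. As the sentence in SAP 8.2 is built, it does not: any value that satisfies the second branch has already satisfied the first.

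The population makes this more than a drafting matter. Inclusion criterion 4 (Protocol 6.2) requires at least two of four abnormal vital signs, and one of the four is "Hypotension with systolic blood pressure (SBP) < 90 mm Hg". Protocol 8.5 places a blood pressure and heart rate reading about one hour after the first dose, when the presenting illness may still dominate. A flag that ignores baseline can then count persisting disease as a post-baseline safety finding, and there is no control arm to show the background rate.

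The rest of the SAP takes baseline into account. A laboratory value is notable only after an increase of at least two grades from baseline (SAP 8.3), and a treatment-emergent AE must be new, more frequent or worse (SAP 8.1).

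**Working it through.** **Logic.** Let A be that the post-baseline value meets the Appendix 4 criterion value, and B that the change from baseline meets the change criterion.

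| A | B | A or (A and B) | A and B |
|---|---|---|---|
| no | no | no | no |
| no | yes | no | no |
| yes | no | **yes** | no |
| yes | yes | yes | yes |

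The third column is identical to A. As a check, the rule was applied to every integer baseline and post-baseline pair from 30 to 220 in each of the six rows: 191 × 191 × 6 = 218,886 pairs. The rule as written differed from the criterion value alone in 0 of them.

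**Can another reading of the sentence rescue it?** It might mean the value alone where Appendix 4 gives only a value, and both where it gives both. Since all six rows give both, that reading amounts to A and B throughout, which is a different rule with different counts. Two reporting tiers may have been intended, but SAP 8.2 describes a single flag and a single incidence.

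**Which entry abnormalities can carry over?** The entry signs of inclusion criterion 4 compare with Appendix 4 as follows.

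- SBP below 90 always lies within the low-SBP limit (≤ 90).
- Heart rate qualifies for entry above 90 bpm but meets the high limit only at 120 or more; entry rates of 91 to 119 do not.
- Temperature and respiratory rate have no row in Appendix 4 and cannot be flagged.

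Diastolic pressure is not an entry sign, but a baseline value beyond its limits behaves in the same way.

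**Worked cases.**

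| Baseline to post-baseline | Change | Rule as written | Both criteria |
|---|---|---|---|
| SBP 88 to 88 | 0 | CN | not CN |
| SBP 84 to 90 | +6 | CN | not CN |
| HR 126 to 121 | −5 | CN | not CN |
| HR 135 to 120 | −15 | CN | not CN |
| SBP 115 to 88 | −27 | CN | CN |
| HR 100 to 121 | +21 | CN | CN |
| SBP 105 to 86 | −19 | CN | not CN |
| HR 106 to 120 | +14 | CN | not CN |
| DBP 64 to 50 | −14 | CN | not CN |

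The first four rows are unchanged or improving values that the present rule counts. The SBP 84 to 90 case also satisfies the SBP component of Clinical Stability (at least 90 mmHg, SAP 9.2), so the same reading is stable for efficacy and notable for safety. The last three rows are new on-treatment values that would be lost if both criteria were simply required.

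**Size.** The documents give no baseline distribution of vital signs, so the number of affected subjects cannot be derived. If the safety denominator lies between the 20 evaluable and 30 enrolled subjects planned in SAP 5.1, one subject moves the overall incidence by 1/30 = 3.3 to 1/20 = 5.0 percentage points.

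**The case against.** The best defence is that a value-only flag is a legitimate and more sensitive screen, and that nothing depends on it. CN vital signs are a descriptive part of the secondary safety endpoint, Protocol 12.8 plans no formal comparisons, and no decision rule uses the flag. The number affected may also be small: hypotension is one of four alternative entry signs, and enrolment is limited to PORT class II and III subjects judged suitable for oral therapy.

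All of this stands as to consequence. It does not explain why Appendix 4 carries a change column that cannot act, and it leaves the programmer to choose between the literal text and the apparent intent. The sensitivity argument also stands, and it counts against simply replacing the rule with both criteria.

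A reader might infer that every abnormal vital sign at entry will be counted as notable. The documents do not support that: only post-baseline readings of SBP, DBP and heart rate can be flagged, and only when they lie beyond an Appendix 4 limit.

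A reader might also infer that persisting disease could not be told apart from a drug effect at all. That goes too far. SAP 8.2 provides change-from-baseline statistics at each time point and a listing of all values of any sign flagged for a subject, and SAP 5 lists all data. With about 30 subjects, an improving value can be recognised in the listing. What the rule blurs is the incidence table.

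**Conclusion.** The point holds as a defect of definition with a limited effect on reporting. That the change column is inert is exact and needs no assumption beyond reading SAP 8.2 literally. The upward effect on the CN incidence needs at least one subject with a baseline value beyond an Appendix 4 limit that is still beyond it after dosing, unchanged or improved. That is plausible given the entry criteria, but its frequency is unknown. Under the assumed denominator of 20 to 30, each such subject adds 3.3 to 5 percentage points. The effect is confined to the CN flag, its incidence summaries and the selection of subjects for the CN listing. The PK analysis is unaffected. This is a minor correction, worth making before the database freeze, by which the SAP introduction says analysis decisions are settled.

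**What to change.** Replace the sentence in SAP 8.2 with two separately labelled tiers, used in both the CN incidence table and the listing flags:

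1. criterion value met;
2. criterion value and change from baseline both met.

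State that tier 2 is the one to read as on-treatment change, and make SAP 10.4 refer to the two tiers.

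The cost is one reworded sentence and one extra row in the table; no new data are needed. Tier 2 alone would miss new values whose change falls just short of the threshold, such as SBP 105 to 86, so tier 1 is kept beside it. No information in the present plan is lost, and the Appendix 4 change column becomes operative.

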8.3 Laboratory Values

Summaries of laboratory data will include hematology, and chemistry, parameters. Laboratory parameters will be presented in alphabetic order with the following exceptions: differentials of white blood cell (WBC) counts will be presented following the WBC results, and chemistry parameters will first be grouped by organ class (renal, liver, electrolytes, and other) and presented alphabetically within each of these classes, as shown below.

Organ Class	Laboratory Parameter
Renal	Creatinine
Renal	Urea
Liver	Alkaline phosphatase (ALP)
Liver	ALT
Liver	AST
Liver	Total Bilirubin
Liver	GGT
Electrolytes	Bicarbonate
Electrolytes	Calcium
Electrolytes	Chloride
Electrolytes	Magnesium
Electrolytes	Potassium
Electrolytes	Sodium
Other	Albumin
Other	Amylase
Other	Blood glucose
Other	Cholesterol
Other	CK
Other	LDH

Table 1.Laboratory Parameters and Organ Class

Organ Class	Laboratory Parameter
Other	Lipase
Other	Phosphate
Other	Total protein
Other	Uric acid

Table 1.Laboratory Parameters and Organ Class

Baseline is defined the local lab value that is closest to and prior to the first dose of study drug.

Several analyses of the laboratory data will be presented. Descriptive statistics (based on International System [SI] units) for chemistry, hematology and the change from baseline will be summarized by treatment group at each time point (EOT Visit and PTE Visit), and for the overall worst value post-baseline (which includes unscheduled visits).

Clinically notable laboratory values will be defined as any lab values with at least a 2-grade increase from baseline. Shift tables will be presented to show the number of subjects with a laboratory value with a grade of 0, 1, 2, 3 or 4 at baseline versus the value at each visit and the worst post-baseline value. Number and percentage of subjects with at least a 2-grade increase from baseline (based on DMID criteria shown in Appendix 3) will be summarized. Percentages for each laboratory test will be based on the number of subjects with a baseline and post-baseline evaluation of the specific laboratory test. A listing will be provided which gives all laboratory results for a given laboratory test for subjects who have at least one 2-grade increase from baseline.

Detailed subject listings of all laboratory data collected during the study will be provided, including calculated creatinine clearance (using the Cockcroft-Gault equation). Laboratory values outside normal limits will be identified in the subject data listings with flags for low (L) and high (H) as will laboratory values that meet the clinically notable thresholds (CN) of at least a 2-grade increase from baseline.

8.4 **Physical Examinations**

Subject listings of all physical examination results by body system will be provided. Any clinically significant changes from baseline will be recorded as adverse events.

9 EXPLORATORY EFFICACY MEASURES

9.1 Investigator's Assessment of Clinical Response

9.1.1 Investigator's Assessment of Clinical Response at EOT

EOT assessments should be performed on the calendar day of, or within 2 days following the last dose of any test article. If a subject withdraws prematurely or terminates participation in the study prior to completion of the planned antibiotic therapy, the EOT visit should be conducted.

The investigator will determine whether or not the subject meets the criteria of 1 of the following clinical outcomes:

Clinical Success: the subject is alive, and the infection is sufficiently resolved such that further antibacterial therapy is not needed. These subjects may have some residual findings related to infection (i.e., cough) requiring ancillary (i.e., non-antibiotic) treatment (e.g., expectorant). For the subject to be considered a Clinical Success at EOT, the subject may not meet any criteria for Clinical Failure or Indeterminate at EOT.

Clinical Failure: the subject requires alternative antibacterial treatment for CABP prior to EOT related to either (a) progression or development of new symptoms of CABP or (b) development of infectious complications of CABP (e.g., empyema, lung abscess) or (c) subject developed an AE that required discontinuation of study therapy. Other reasons for Clinical Failure are:

- Subject is receiving antibacterial therapy that may be effective for the infection under study for a different infection from the 1 under study.
- Death prior to EOT visit.
- Other specified reason.

Indeterminate: the clinical response to test article could not be adequately inferred due to:

- Subjects were not seen for EOT evaluation because they withdrew consent or were lost to follow-up,
- Other specified reason.

9.1.2 Investigator's Assessment of Clinical Response at PTE

The PTE assessment is to be performed 5 to 10 days after the subject's last day of therapy. The investigator will determine whether or not the subject meets the criteria of 1 of the following clinical outcomes:

Clinical Success: survival after completion of a test article regimen without receiving any systemic antibacterial therapy other than test article, resolution of signs and symptoms of the infection present at Screening with no new symptoms or complications attributable to CABP and no need for further antibacterial therapy.

Clinical Failure: the subject requires alternative antibacterial treatment for CABP prior to PTE related to either (a) progression or development of new symptoms of CABP or (b) development of infectious complications of CABP (e.g., empyema, lung abscess).

- The subject is receiving antibiotics that may be effective for the infection under study for a different infection from the 1 under study.
- Death prior to PTE.
- Other specified reason.

Indeterminate: the clinical response to test article could not be adequately inferred due to:

- Subjects were not seen for PTE evaluation because they withdrew consent or were lost to follow-up.
- Other specified reason.

9.2 Clinical Stability

The formal determination of the subject's Clinical Stability will be done programmatically using the investigator's assessment of the subject's vital signs entered into the eCRF. The investigator is not responsible for categorizing the subject's Clinical Stability. Clinical Stability will be determined daily and analyzed by day, early clinical response window, EOT, and PTE.

Patients will be considered clinically stable if they achieve all the following criteria:

- temperature $\leq 37.8^{\circ}$ C (100°F);
- heart rate ≤ 100 beats/minute;
- RR \leq 24 breaths/minute;
- systolic blood pressure \geq 90 mmHg; and
- arterial oxygen saturation $\ge 90\%$ or PaO2 ≥ 60 mmHg on room air.

9.3 Clinical Outcomes

The number and percentage of subjects classified as a Clinical Success, Clinical Failure, and Indeterminate by the Investigator's Assessment at EOT in the ITT population will be presented. The number and percentage of subjects in each response category for the overall assessment of Clinical response at PTE (based on the investigator's assessment) in the ITT population will also be presented. The number and percentage of subjects with stabilization of all vital signs associated with CABP at EOT will be presented for the ITT population as will the number and percentage of subjects with stabilization of each vital sign. These include temperature (no fever or hypothermia), SBP (> 90 mmHg), heart rate (< 90 bpm), RR (< 20 breaths/minutes), and PaO₂ (> 60 mmHg by pulse oximetry or ABG). WBC count (< 12,000 cells/mm³ or \geq 4,000 cells/mm³) and immature neutrophils (< 15%).

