6.2 Demographics and Baseline Characteristics

Except where indicated, demographic data and baseline characteristics will be presented for the ITT population. A table will present the subject demographics (e.g., gender, age, ethnicity, and race) and baseline characteristics (height, weight, BMI, and creatinine clearance categorized before the start of test article as:

- severe renal impairment [< 30 mL/min],
- moderate renal impairment [30-50 mL/min],
- mild renal impairment [> 50-80 mL/min], and
- normal renal function [> 80 mL/min]).

Age will be calculated from the date of birth to the informed consent date. Age will be summarized as a continuous variable and in the categories, 18-45, >45-65, and >65 years.

Creatinine clearance will be calculated from the local laboratory data since these data were used for determination of the inclusion and exclusion criteria and will be determined from the Cockcroft-Gault equation.

A table will provide the frequency counts and percentages for subjects who received prior antibiotics, and PORT Risk Class (from the eCRF) for the ITT population. PORT score will also be summarized as a continuous variable.

Baseline assessments of clinical symptoms, clinical signs, abnormal vital signs, and abnormal laboratory signs of CABP will be presented for the ITT, and PK populations.

The number and percentage of subjects with each of the CABP symptoms (cough, pleuritic chest pain, dyspnea, and phlegm/sputum production) by severity (absent, mild, moderate, severe) will be presented. The number and percentage of subjects with the presence by severity (i.e., absent, mild, moderate, severe) of the following clinical signs will be provided: rales, rhonchi, dullness on percussion, bronchial breath sounds, wheezing, decreased breath sounds, and egophony. The number and percentage of subjects with fever (defined as body temperature > 38°C [100.4°F] oral or rectal), hypothermia (defined as body temperature < 36°C [95.5°F] oral or rectal), hypotension with systolic blood pressure < 90 mmHg, heart rate > 90 bpm, respiratory rate > 20 breaths/min, hypoxemia (defined as PaO₂ < 60 mmHg by arterial blood gas or oxygen saturation < 90% by pulse oximetry), elevated total WBC count (> 12,000 cells/mm³), leucopenia (WBC < 4,000 cells/mm³), elevated immature neutrophils (> 15% band forms regardless of total peripheral WBC count) and any of elevated total WBC count, leucopenia or elevated immature neutrophils will be summarized.

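### The EOT stabilization limits in SAP 9.3 are not the complements of the abnormal limits in SAP 6.2, so boundary readings that were never abnormal by those limits count as not stabilized (minor)

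*SAP*

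**What the plan says.** Three parts of the plan classify the same vital signs.

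- **Abnormal at entry.** SAP 6.2 tabulates baseline "hypotension with systolic blood pressure < 90 mmHg, heart rate > 90 bpm, respiratory rate > 20 breaths/min". These are the limits of protocol inclusion criterion 4: "Hypotension with systolic blood pressure (SBP) < 90 mm Hg", "Heart rate > 90 beats per minute (bpm" and "Respiratory rate (RR) > 20 breaths/minute". SAP 6.2 and inclusion criterion 5 add PaO2 below 60 mmHg by ABG or saturation below 90% by pulse oximetry, WBC above 12,000 or below 4,000 cells/mm³, and bands above 15%.
- **Stabilized at EOT.** SAP 9.3 says that the number and percentage with "stabilization of all vital signs associated with CABP at EOT will be presented for the ITT population", and also gives the result for each sign. The limits include "SBP (> 90 mmHg), heart rate (< 90 bpm), RR (< 20 breaths/minutes", together with no fever or hypothermia, PaO2 above 60 mmHg by either pulse oximetry or ABG, WBC below 12,000 or at least 4,000, and bands below 15%.
- **Clinical Stability.** SAP 9.2 states: "Patients will be considered clinically stable if they achieve all the following criteria". The list includes "heart rate ≤ 100 beats/minute", respiratory rate up to 24, SBP of at least 90, temperature up to 37.8°C, and saturation of at least 90% or PaO2 of at least 60 mmHg on room air. EOT is one of its analysis visits.

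**The concern.** SAP 9.3 describes its signs as those associated with CABP and follows the entry-criterion list, so the natural reading is that stabilized means no longer abnormal. Temperature is written exactly that way. The other signs are not: both the abnormal and the stabilized limits are strict, and the boundary value belongs to neither.

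Take a subject with respiratory rate 20 at Screening and at EOT. That rate never met the abnormal limit, yet SAP 9.3 reports it as not stabilized and the subject fails the all-signs result. These classifications are programmed from the text, so the gap would pass straight into the table and could only lower the reported rate.

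Clinical Stability at EOT, with different limits, is reported for the same visit. The SAP does not say how the two results relate.

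**Working it through.** The plan states no figure to reproduce. The check compares the limits, then sizes the gap under stated assumptions.

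**Step 1. Limits side by side (integer readings)**

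| Sign | Abnormal (SAP 6.2) | Stabilized (SAP 9.3) | Neither |
|---|---|---|---|
| SBP, mmHg | < 90 | > 90 | 90 |
| Heart rate, bpm | > 90 | < 90 | 90 |
| Respiratory rate, /min | > 20 | < 20 | 20 |
| PaO2, mmHg | < 60 | > 60 | 60 |
| Bands, % | > 15 | < 15 | 15 |
| Temperature, °C | > 38.0 or < 36.0 | no fever or hypothermia | none |
| WBC, cells/mm³ | > 12,000 or < 4,000 | < 12,000 or ≥ 4,000 | none |

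No SBP, heart rate, respiratory rate, PaO2 or band value is both abnormal and stabilized, so for these the fault runs in one direction only. WBC fails differently: any value of 12,000 or more is also at least 4,000, and any value under 4,000 is also under 12,000, so every value passes.

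The oxygen rule has a further fault. It gives a PaO2 limit for pulse oximetry, which measures saturation, and gives no saturation limit. The Schedule of Events lists ABG at Screening only (with pulse oximetry as the alternative) and pulse oximetry at EOT, so the written limit does not fit the measurement scheduled for that visit.

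**Step 2. Size for SBP, heart rate and respiratory rate together**

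The documents give no EOT distribution. Assume independent normal values rounded to integers, with SBP mean 122 and SD 14 throughout; heart rate (HR) and respiratory rate (RR) vary by setting. With m the mean and s the SD:

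- SAP 9.3: Φ((89.5 − m_HR)/s_HR) × Φ((19.5 − m_RR)/s_RR) × [1 − Φ((90.5 − 122)/14)]
- Complement of SAP 6.2: Φ((90.5 − m_HR)/s_HR) × Φ((20.5 − m_RR)/s_RR) × [1 − Φ((89.5 − 122)/14)]

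For heart rate 80 (SD 12) and respiratory rate 18 (SD 2):

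- SAP 9.3: 0.7857 × 0.7734 × 0.9878 = 0.600
- Complement: 0.8092 × 0.8944 × 0.9899 = 0.716
- Difference: 11.6 points

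| HR mean/SD | RR mean/SD | SAP 9.3 | Complement | Gap, points | P(RR = 20) | P(HR = 90) |
|---|---|---|---|---|---|---|
| 80/12 | 18/2 | 60.0% | 71.6% | 11.6 | 12.1% | 2.4% |
| 82/12 | 18/2.5 | 52.6% | 63.3% | 10.7 | 11.6% | 2.7% |
| 78/10 | 17/2 | 77.3% | 85.0% | 7.7 | 6.6% | 1.9% |
| 78/10 | 16/2 | 83.0% | 87.4% | 4.5 | 2.8% | 1.9% |
| 75/10 | 16/2 | 87.8% | 91.9% | 4.0 | 2.8% | 1.3% |
| 75/10 | 16/1.5 | 90.6% | 92.9% | 2.2 | 0.9% | 1.3% |

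Gaps are taken before rounding. SBP exactly 90 has probability 0.2% in every setting. Respiratory rate 20 is the larger contributor in all settings but the last. In 30 subjects the gap is 0.022 × 30 = 0.7 to 0.116 × 30 = 3.5 subjects.

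**Step 3. SAP 9.3 against SAP 9.2**

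Heart rate 90–100, respiratory rate 20–24, SBP 90, PaO2 60 and temperature below 36.0°C are stable under SAP 9.2 but not stabilized under SAP 9.3. Temperature 37.9–38.0°C is the reverse. Writing SAP 9.3 as the complement of SAP 6.2 removes the boundary cases but leaves heart rate 91–100, respiratory rate 21–24 and both temperature differences.

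**The case against.** The strongest reply is that little depends on this. The summary is exploratory, descriptive and single-arm; the protocol plans no formal comparisons; all data are listed, so the table can be re-derived. All of that stands, and it is why the point is minor.

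The size is also open to challenge. A reader might infer from the settings with mean respiratory rate 17 or 18 that the loss is 8 to 12 points. The documents do not support that as a finding: at mean 16 the same calculation gives about 2 to 5. Nor do they say how often a rate of exactly 20 is recorded.

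Two further readings go too far:

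- **That SAP 9.2 is a looser version of the same result, so the SAP contradicts itself.** SAP 9.2 is wider for heart rate and respiratory rate, but its upper temperature limit (37.8°C) is stricter than no fever (38°C), and it requires room air. The two rules are not nested. They have different names, and two descriptive measures with different limits are not in themselves an error. What is missing is a clear label.
- **That SBP 90 is normal throughout the SAP.** Appendix 4 uses SBP of 90 or less as the criterion value for a clinically notable low reading. The statement that SBP 90 is not abnormal holds for SAP 6.2 and inclusion criterion 4 only.

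None of this closes the gap between SAP 6.2 and SAP 9.3.

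**Conclusion.** The point holds as a minor inconsistency in wording. By the limits of SAP 6.2 and inclusion criteria 4 and 5, SBP 90, heart rate 90, respiratory rate 20, PaO2 60 and bands 15% are not abnormal, yet SAP 9.3 counts them as not stabilized. For the vital signs this lowers the all-signs result. For bands it lowers the separate result; whether WBC and bands also enter the all-signs summary is not clear from the text. The WBC rule excludes nobody.

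The mismatch follows from the text alone. Its size does not: about 2 to 12 points, or roughly 1 to 4 of 30 subjects, under assumed independent, rounded normal values for three signs. Temperature and oxygenation are left out of that calculation. The primary PK comparison and the sample size are not affected.

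**What to change.** Reconcile SAP 9.3 with SAP 6.2 by writing each limit as the exact complement of the abnormal limit:

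- SBP ≥ 90 mmHg, heart rate ≤ 90 bpm, respiratory rate ≤ 20 breaths/min;
- PaO2 ≥ 60 mmHg by ABG, or oxygen saturation ≥ 90% by pulse oximetry;
- WBC ≥ 4,000 **and** ≤ 12,000 cells/mm³;
- bands ≤ 15%.

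State whether WBC and bands belong to the all-signs summary. Title the table as absence of the entry-criterion abnormalities at EOT, and add a sentence that it differs from Clinical Stability (SAP 9.2), whose limits are wider for heart rate and respiratory rate and stricter for upper temperature. The new limits alone would not separate the two results; the title does that.

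This changes an analysis classification, using limits already in the documents. It makes no judgment on which limits are clinically preferable and changes no eligibility or treatment rule. The cost is SAP wording and the matching program specification, before database freeze.
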